#### Illustration of dose adjustment algorithm

	Treatment		HemoCue		(FL_A)	(FL_B)	(FL_C)
Visit	Start date/		Hgb	Dose	Adjust-	Over	Inter-
(Example)	Stop date	Duration	(g/dL)	(mg)	ment	13 g/dL	ruption
Day 1	01FEB2017/	29	11.1	4	Ν	Ν	Ν
-	01MAR2017						
Week 4	02MAR2017/	14	11.4	4	Ν	Ν	Ν

#### 204716

#### CONFIDENTIAL

Dose A	djustment								
		15MAR2017							
	Week 8	02APR2017/	30	11.8	2	Y	N	N	
		01MAY2017							
	Week 12	02MAY2017/	31	13.4	0	Y	Y	Y	
		01JUN2017		44.0		N (			
	Week 16	02JUN2017/ 01JUL2017	30	11.6	1	Y	N	N	
	Week 20	02JUL2017/	31	12.7	0	Y	Ν	Y	
		01AUG2017							
	Week 24	-	-	12.3	-	-	Ν	-	

 
'Dose adjustment'
 
Duration (days) of treatment interruption due to Hgb >13 g/dL
 
									
Calculation of duration of treatment interruption due to Hgb >13 g/dL will be based on the above									
algorithm and the below formula.									

 
Duration (days) = Sum of [Duration]n
 
									
	where								
	[Duration]₀ represents exposure duration at visit n.								
If over 13 g/dL flag (FL_B) = 'Y' and interruption flag (FL_C) = 'Y':									

 
Duration (days) = Treatment Stop Date - Treatment Start Date + 1
 
									
If else:									

 
Duration (days) = 0
 
									
Frequency of dose adjustment									
Calculation of frequency of dose adjustment will be based on the above algorithm.									

 
Number of dose adjustment will be counted for each subject as follows:
 
									

 
Counts of adjustment flag = 'Y'
 
									
Number of dose adjustment to reach the lower Hgb target (10.0 g/dL)									
Number of dose adjustment to reach the lower Hgb target will be counted for each subject as follows									
• Counts of adjustment flag ='Y' at visits before Date to reach the lower Hgb target, including a record which firstly achieved the lower Hgb target.									

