3. OBJECTIVES AND ENDPOINTS

Objectives	Endpoints
Primary	

 To characterize the appropriateness of the starting dose of GSK1278863 in HD patients not using ESAs 	
 Change from baseline in Hgb at Week 4 Number (%) of subjects by Hgb change from baseline category at Week 4
Secondary	

 To characterize overall Hgb control of GSK1278863 in HD patients not using ESAs 	
 Hgb and changes from baseline Number (%) of subjects who have a Hgb level within the target range (10.0–12.0 g/dL) Time (in days) to reach the lower target Hgb level (10.0 g/dL) Number (%) of subjects who have a Hgb level of less than 7.5 g/dL Number (%) of subjects who have a Hgb increase of more than 2 g/dL over any 4 weeks Number (%) of subjects who have a Hgb level of more than 13.0 g/dL and number of episodes

 To characterize the PK of GSK1278863 	
 AUC and Cmax of plasma GSK1278863

 To characterize the effect on iron use of GSK1278863 	
 Dose of intravenous iron Number (%) of subjects who used intravenous iron

 To characterize the effect on iron metabolism of GSK1278863 	
 Change from baseline in ferritin Change from baseline in TSAT Changes from baseline in hepcidin, serum iron, and TIBC

 To characterize dose adjustment of GSK1278863 	
 Distribution of dose level Duration of treatment interruption due to Hgb > 13 g/dL Frequency of dose adjustments
Safety	

 To assess the safety and tolerability of GSK1278863 	
 Incidence and severity of AEs and SAEs, including AESIs Reasons for discontinuation of study medication Laboratory tests, ECG, vital signs, and ophthalmology assessments

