6.3. Treatment Schedule

Starting dose (Day 1 to Week 4)

In the Japanese HD patients not using ESAs enrolled in the study, oral administration of GSK1278863 once daily at the starting dose of 4 mg will be started (Day 1), and continued until the day of Week 4.

Maintenance Dose (Week 4 to Week 24)

From Weeks 4 to 24, interruption of treatment or dose adjustments will be made within the maintenance dose range of 1-24 mg (Table 4) according to the dose adjustment algorithm (Table 5) to achieve and/or maintain Hgb within the target range (10.0-12.0 g/dL) based on the HemoCue Hgb value measured every 4 weeks. Dose changes will be made every 4 weeks. If any of the one-step dose reduction criteria is met during treatment at the minimum maintenance dose (1 mg), treatment should be interrupted; once the one-step dose increase criteria are met, treatment at 1 mg will be resumed. If the one-step dose increase criterion is met during treatment at the maximum maintenance dose (24 mg), treatment at 24 mg should be continued.

Table 4 Maintenance Dose of GSK1278863

Dose step	1	2	3	4	5	6	7	8
Dose level of GSK1278863 (once daily)	1 mg	2 mg	4 mg	6 mg	8 mg	12 mg	18 mg	24 mg
Number of GSK1278863 tablets taken	1 mg tablet ×1	2 mg tablet ×1	4 mg tablet ×1	6 mg tablet ×1	4 mg tablet ×2	6 mg tablet ×2	6 mg tablet ×3	6 mg tablet ×4

Table 5 Dose Adjustment Algorithm (GSK1278863)

Hgb (g/dL)	Hgb increase over 4 weeks (g/dL)	Treatment
>13.0	NA	Interrupt treatment until Hgb decreases to less than 12.0 g/dL Resume treatment at the one lower dose level (resume treatment at 1 mg once the one-step dose increase criteria are met, if interrupted at 1 mg)
12.0-13.0	NA	One-step dose reduction
10.0-<12.0	>2.0	One-step dose reduction
	≤2.0	Continue treatment at the current dose level
7.5-<10.0	>2.0	One-step dose reduction
	0.5-2.0	Continue treatment at the current dose level
	<0.5	One-step dose increase
<7.5	NA	Discontinue treatment permanently * and initiate another appropriate treatment

*: If an initial Hgb value is less than 7.5 g/dL, measurement will be repeated at the same study visit (using the same sample) to calculate the average. If the average meets the Hgb stopping criteria, study treatment will be discontinued.

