7.1. Time and Events Table

Time and Events Tables are provided in Table 6 and Table 7 for the overall study and for pharmacokinetic assessments. For subjects on dialysis twice or more per week, throughout the study period, including the screening, treatment and follow-up periods, the study visit days should occur on the first dialysis session day of the week (e.g., if Monday-Wednesday-Friday schedule, the study visit should be on Monday). Visit days are counted from the day of first dose of study treatment (Day 1). To allow for a flexible schedule, the allowable window for Screening Visit will be “4 weeks \pm 7 days prior to Day 1”, and that for the visits after Day 1 will be “ \pm 3 days”. In any case, the study visit should occur on the first dialysis session day of the week. Unless otherwise specified, all assessments should occur before dialysis on the day.

Table 6 Time and Events Table

Period	Screening		Treatment							Follow-up	
Visits All assessments pre-dialysis, unless noted.		Week -4	Day 1	Week 4	Week 8	Week 12	Week 16	Week 20	Week 24	Early withdrawal ¹⁰	2–4 weeks after Week 24 or early withdrawal
Allowable window (days)		±7	-	±3	±3	±3	±3	±3	±3	-	±3
Informed consent	X										
Inclusion/exclusion		X	X								
Medical history, demography, height, body weight ¹		X									
Interactive Web Recognition System (IWRS) call		X	X	X	X	X	X	X	X	X	X
Study medication dispensing ²			X	X	X	X	X	X			
Study medication compliance				X	X	X	X	X	X	X	
Vital signs (before and after dialysis) ³		X	X	X		X			X	X	X
Ophthalmology examination ⁴		X ¹¹				↔	↔	↔	↔	↔	
ECG		X				X			X		
HemoCue Hgb			X	X	X	X	X	X	X		
Hematology		X ¹²	X	X	Hgb only	X	Hgb only	Hgb only	X	X	X
Clinical chemistry		X	X	X		X			X	X	X
Ferritin, TSAT		X	X	X		X			X	X	
Serum iron, TIBC, Unsaturated iron Binding Capacity (UIBC), serum transferrin, hepcidin			X	X		X			X	X	
Serum pregnancy test ⁵		X	X	X		X			X	X	X
Estradiol ⁵ , FSH ⁶		X									
Pharmacokinetics ⁷						X			X		
Intact Parathyroid Hormone (iPTH)			X	X		X			X		
Genetics sample ⁸			X								
Adverse event assessment ⁹											→
Concomitant medication assessment											→

1. Body weight is measured after dialysis.
2. If a subject visit the study site only to receive study medication, only the IWRS call, study medication dispensing, and study medication compliance will be required
3. At visits without dialysis, only one measurement of each parameter will be obtained.
4. Ophthalmology exams should be conducted at the following time points.

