9.4.2. Safety Analysis

9.4.2.1. Exposure

Exposure information will be listed for all subjects. The duration of treatment (number of days), cumulative dose will be tabulated. In addition, distribution of the dose level at each assessment visit and final assessment visit will be tabulated. Frequency of dose adjustment and duration of treatment interruption due to Hgb >13 g/dL will be summarized.

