#### Extent of Exposure

- Number of days of exposure to study drug will be calculated based on the formula: Duration of Exposure in Days = Sum of [Exposure Duration at Each Visit] where Exposure Duration at Each Visit = Treatment Stop date - Treatment Start date + 1 If dose is interrupted in a visit according to dose adjustment algorithm, duration in the period will be included in duration of exposure.
- Cumulative dose will be based on the formula using prescribed dose: Cumulative Dose = Sum of (Exposure Duration x Dose) at Each Visit
- Daily Dose
  - Cumulative Dose / Duration of Exposure in Days

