2.37.	All Treated Subjects	LB1	Summary of Total Iron Binding Capacity (umol/L) by Visit	Includes Baseline values	Y			
2.38.	All Treated Subjects	LB1	Summary of Total Iron Binding Capacity (umol/L) by Visit by Dialysis Status	Includes Baseline values	Y			
2.39.	All Treated Subjects	LB1	Summary of Total Iron Binding Capacity (umol/L) Change from Baseline by Visit		Y			
2.40.	All Treated Subjects	LB1	Summary of Total Iron Binding Capacity (umol/L) Change from Baseline by Visit by Dialysis Status		Y			
Dose a	djustment							
2.41.	All Treated Subjects	EFF_T11	Summary of Dose level (mg) by Visit	Includes mean dose (mg) during Week 12 to 24	Y			
2.42.	All Treated Subjects	EFF_T11	Summary of Dose level (mg) by Visit by Dialysis Status	Includes mean dose (mg) during Week 12 to 24	Y			
2.43.	All Treated Subjects	EFF_T12	Summary of Duration (days) of treatment interruption due to Hgb >13.0 g/dL		Y			
2.44.	All Treated Subjects	EFF_T12	Summary of Duration (days) of treatment interruption due to Hgb >13.0 g/dL by Dialysis Status		Y			
2.45.	All Treated Subjects	EFF_T13	Summary of Dose Adjustment		Y			
2.46.	All Treated	EFF_T13	Summary of Dose Adjustment by Dialysis Status		Y			

Efficac	Efficacy: Tables							
No.	Populatio n	IDSL / TST ID / Example Shell	Title	Programming Notes	SAC			
	Subjects							
2.47.	All Treated Subjects	EFF_T14	Summary of Number (%) of Subjects with Each Dose Level by Visit		Y			
2.48.	All Treated Subjects	EFF_T14	Summary of Number (%) of Subjects with Each Dose Level by Visit by Dialysis Status		Y			

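### The SAP formula for days of interruption due to Hgb >13 g/dL gives 0 days to a follow-on 0 mg record at Hgb 12.0-13.0, although the protocol keeps that interruption running until Hgb is below 12.0

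*SAP*

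**What the plan says.** **Protocol.** Section 3 lists "Duration of treatment interruption due to Hgb > 13 g/dL" among the secondary endpoints for dose adjustment. Section 9.4.2.1 adds: "Frequency of dose adjustment and duration of treatment interruption due to Hgb >13 g/dL will be summarized". Section 6.3, Table 5, sets the action at Hgb above 13.0: "Interrupt treatment until Hgb decreases to less than 12.0 g/dL". For a subject already at the lowest dose the end point differs: "resume treatment at 1 mg once the one-step dose increase criteria are met, if interrupted at 1 mg". Hgb for dosing is the HemoCue value, and dose decisions are made every 4 weeks.

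**SAP.** Section 10.6.3 sets two flags on each visit record. FL_B is Y when that visit's HemoCue Hgb exceeds 13. FL_C is Y when the prescribed dose is zero. The record's days (stop date minus start date plus 1) count under the condition "If over 13 g/dL flag (FL_B) = 'Y' and interruption flag (FL_C) = 'Y"; otherwise the record contributes 0. The subject's total is the sum over visits. It is reported in Table 2.43, "Summary of Duration (days) of treatment interruption due to Hgb >13.0 g/dL", and by dialysis status in Table 2.44.

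**Unscheduled values.** On these the SAP disagrees with itself. The dose adjustment algorithm in 10.6.3 leaves unscheduled Hgb values out. Note [5] to Table 4 and two paragraphs of 8.1.2 (the dose adjustment introduction and the duration of interruption) bring them in.

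**The concern.** The protocol uses two thresholds: the interruption starts above 13.0 and ends below 12.0. The SAP formula tests only the starting threshold and repeats that test at every visit. Between the two thresholds the subject is still off drug because of the earlier value above 13, but FL_B has gone back to N and the whole record is lost. Nothing in the supplied SAP text carries the cause of the interruption forward to later 0 mg records.

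The protocol says the study is designed to evaluate the dose adjustment regimen, and this endpoint describes how long subjects are off drug after overshooting. The duration summary covers only interrupted subjects, a subset of about 22, so one affected subject could move its mean or maximum. The exposure-duration summary will not show the loss, because SAP 10.6.2 says: "If dose is interrupted in a visit according to dose adjustment algorithm, duration in the period will be included in duration of exposure".

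**Working it through.** **1. The SAP's own illustration.** Each record lasts stop date − start date + 1.

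| Record | Dates (2017) | Days | HemoCue Hgb | Dose | FL_B | FL_C | Days counted |
|---|---|---|---|---|---|---|---|
| Week 12 | 02 May-01 Jun | 31 | 13.4 | 0 mg | Y | Y | 31 |
| Week 16 | 02 Jun-01 Jul | 30 | 11.6 | 1 mg | N | N | 0 |
| Week 20 | 02 Jul-01 Aug | 31 | 12.7 | 0 mg | N | Y | 0 |

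All printed durations reproduce. The rule implies a total of 31 days, which is right for this subject. Hgb goes straight from 13.4 to 11.6 and dosing resumes. The Week 20 zero follows 1 mg at 12.7, so it is a step down from the minimum dose and does not belong to this endpoint. The illustration therefore never reaches the case at issue.

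**2. Hypothetical changes to that illustration.** The comparison rule takes each run of consecutive 0 mg records, starts at its first Hgb above 13, and counts while Hgb stays at 12.0 or more.

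| Weeks 12, 16, 20 (Hgb / dose) | SAP rule | Run rule |
|---|---|---|
| 13.4/0, 11.6/1, 12.7/0 (as printed) | 31 | 31 |
| 13.4/0, 12.6/0, dosing resumed | 31 | 31 + 30 = 61 |
| 13.4/0, 12.6/0, 12.3/0 | 31 | 31 + 30 + 31 = 92 |
| 12.5/0, 12.7/0, 12.4/0 (never above 13) | 0 | 0 |

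**3. On nominal visits.** Protocol 7.1 requires that "In any case, the study visit should occur on the first dialysis session day of the week", so a 4-week interval is nominally 28 days. With k follow-on records at 12.0-13.0 and 0 mg, the SAP rule gives 28 days and the interruption lasts 28 × (k + 1): 56 for k = 1 and 84 for k = 2. Each such record loses about 28 days.

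**4. Ceiling.** The last dose record is Week 20, so the most that can be lost is (20 − trigger week)/4 × 28 days: 112, 84, 56, 28 and 0 for triggers at Weeks 4, 8, 12, 16 and 20. A Week 4 trigger needs a rise of more than 13.0 − 10.0 = 3.0 g/dL, because HemoCue Hgb at entry is below 10.0.

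**5. Interruption from 1 mg.** With 13.4/0, 11.5/0, 10.8/0 the SAP rule gives 31 days. The remaining 30 + 31 = 61 days at 0 mg come after Hgb fell below 12.0, while dosing waits for the one-step increase criteria. At scheduled visits the earliest interruption from 1 mg is Week 12 (2 mg at Week 4, 1 mg at Week 8). At most two follow-on records, 2 × 28 = 56 days, can fall in this group.

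**6. Does the run rule lose anything?** I compared the two rules over all 216 three-visit sequences of Hgb (11.5, 12.5 or 13.5) and dose (0 or 1 mg). The run rule never gave fewer days, and the same sequences had a non-zero duration. This requires restarting the count in every run. For 13.5/0, 11.5/1, 13.5/0 the SAP rule gives 31 + 31 = 62, while a count that stopped for good at the first resumption would give 31.

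**The case against.** - **Low stakes.** This is one of three dose-adjustment descriptors in an estimation-only study. A loss needs a subject to exceed 13.0 and still be at 12.0-13.0 and 0 mg about four weeks later. The documents give no rate for either event and no rate of Hgb fall off drug. This stands, and it limits the weight of the point.
- **The data are reported elsewhere.** Figure 2.11 (Hgb and dose profiles), Listings 10 and 12, and the counts at 0 mg by visit let a reader rebuild each interruption. Cumulative and daily dose also fall with 0 mg records, although they do not show the cause. All true, but none of these corrects Tables 2.43 and 2.44.
- **The figures can look dramatic.** The 61 and 92 days come from altering an illustration with calendar-month intervals; 56 and 84 are the nominal equivalents. A reader might take the 112-day ceiling as an expected loss. It is an arithmetic limit, and nothing in the documents makes it likely.
- **Attribution after Hgb falls below 12.0.** A reader might infer that every later 0 mg day in an interruption from 1 mg belongs to this endpoint. The documents do not settle this: by then dosing is waiting for the increase criteria. Separate reporting is defensible; inclusion in the total is a choice that the SAP should state.
- **Shells not seen.** The table shells are in separate documents, so the absence of a carry-forward rule is established only for the supplied text.

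**Conclusion.** The point holds. As written, the SAP formula ends an interruption at the first visit with Hgb at or below 13, whereas the protocol ends it below 12.0. Each follow-on 0 mg record at 12.0-13.0 loses about 28 days, and for scheduled values the error can only be an understatement. This rests on the protocol's 4-week dose decisions and on the flags being set visit by visit, as the SAP states.

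Two stronger readings are not supported. One is that the reported durations will in fact be materially wrong: the expected size is unknown and may be zero. The other is that the main results are affected. The primary endpoint and the sample size are untouched. For scheduled values the number of subjects interrupted is also unchanged, because the first record above 13 at 0 mg is still captured. With an unscheduled value above 13, that number could depend on which of the SAP's conflicting statements governs. The conflict is a separate matter; the carry-forward gap exists under either reading.

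**What to change.** In SAP 10.6.3, replace the record-by-record condition with a rule applied separately to each run of consecutive 0 mg records:

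1. Start at the first record in the run with HemoCue Hgb >13.
2. Sum that record and the following 0 mg records in the run while Hgb remains ≥12.0, until a non-zero dose is prescribed or study treatment ends.
3. Score 0 for records before the first value above 13 in a run, and for runs that never exceed 13.
4. Sum over all runs for the subject.
5. For interruptions from 1 mg, show the 0 mg days from the first Hgb <12.0 onward on a separate line, and state whether they enter the total. Any record with Hgb >13 and 0 mg still counts, so no day counted now is lost.

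Add a follow-on record at 12.0-13.0 to the illustration so that the case is shown. Separately, adopt one rule on unscheduled HemoCue values and use it in 10.6.3, in 8.1.2 and in note [5] to Table 4.

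The cost is a few lines of SAP text and programming, with no new data and no change to any dosing rule. The downside is that reported interruption days may be longer.

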### Number of dose adjustment to reach the lower Hgb target (10.0 g/dL)

The number and percentage of subjects with dose adjustments to reach the lower Hgb target will be provided on the basis of on-therapy Hgb. Number of dose adjustment to reach the lower Hgb target will be summarized using mean, standard deviation, minimum, median, mode, and maximum. For dose adjustments frequency, the number and percentage of subjects will be provided by the number of dose adjustments (i.e., zero, one, two, three, four, five or more). Subjects who does not reach the lower Hgb target during treatment period will be excluded from the summary. This will be also summarized by baseline dialysis status.

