#### Dose Adjustment

#### Dose adjustment algorithm

- Dose Adjustment algorithm will be based on HemoCue Hgb values at scheduled visits. No Hgb values measured at unscheduled visits will be included.
- Dose will be derived from prescribed dose recorded in eCRF, not actual dose associated with container numbers.
- The following table illustrates the algorithm using analysis flags as below:
  - (FL\_A): Adjustment flags will be counted if prescribed dose recorded in eCRF is changed from that of the previous visit.
  - (FL\_B): Over 13 g/dL flags will be counted if HemoCue Hgb >13 g/dL is observed.
  - (FL\_C): Interruption flags will be counted if prescribed dose recorded in eCRF is zero. Treatment durations will be calculated based on the following formula:
    - Duration (days) = Treatment Stop Date Treatment Start Date + 1

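### The count of dose adjustments needed to reach 10.0 g/dL includes the dose change made at the visit where the target was already met, adding one for subjects whose dose is changed at that visit

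*SAP*

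**What the plan says.** SAP 10.6.3 (Number of dose adjustment to reach the lower Hgb target) adds up adjustment flags equal to Y at visits before the date of reaching 10.0 g/dL, "including a record which firstly achieved the lower Hgb target".

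The flag (FL_A) is defined in the same section: "Adjustment flags will be counted if prescribed dose recorded in eCRF is changed from that of the previous visit". Increases, reductions and interruptions all qualify.

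SAP 8.1.2 sets the reporting: "Number of dose adjustment to reach the lower Hgb target will be summarized using mean, standard deviation, minimum, median, mode, and maximum". Subjects are also tabulated by number of adjustments, from zero to five or more. Subjects who never reach 10.0 g/dL are left out.

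Protocol 6.3 fixes the starting dose of 4 mg, which is "continued until the day of Week 4". Later changes follow Protocol Table 5, "based on the HemoCue Hgb value measured every 4 weeks".

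**The concern.** A count of adjustments made to reach a target should stop at the last dose decision that could have influenced reaching it. By including the record on which the target is first met, the rule picks up the decision taken at that visit in response to the Hgb just measured.

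The clearest case is Week 4. The dose is fixed until then, so anyone who reaches 10.0 g/dL at Week 4 did so with no adjustments, by design. If that subject has overshot and the dose is cut or interrupted at Week 4, the rule reports one adjustment to reach the lower target. A downward step for over-response is then shown as titration that was needed.

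The primary objective is the appropriateness of the starting dose. In a study of 22 enrolled subjects, a few such counts would visibly move the zero category, the mean and the maximum.

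**Working it through.** **What a record holds.** In the SAP table titled "Illustration of dose adjustment algorithm", the Day 1 dosing interval ends on 01MAR2017 and the Week 4 interval starts on 02MAR2017. The Week 12 row shows Hgb 13.4, dose 0 mg and flag Y. The row's dose follows the row's Hgb.

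**Reproducing the plan's flags.** The illustrated doses from Day 1 to Week 20 are 4, 4, 2, 0, 1, 0. Flagging each dose that differs from the previous one gives N, N, Y, Y, Y, Y, as printed. The first on-therapy Hgb of at least 10.0 is at Week 4 (11.4, flag N). The count is 0 with or without that record, so the illustration does not expose the problem.

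**When the reaching record carries a Y.** In Protocol Table 5, Hgb of 10.0 to below 12.0 with a rise of 2.0 or less means "Continue treatment at the current dose level", so the flag is N. A rise above 2.0, or Hgb of 12.0 to 13.0, triggers a "one-step dose reduction". Hgb above 13.0 triggers an interruption. Both give Y. At Week 4, entry Hgb is below 10.0, so any value of 12.0 or more is also a rise above 2.0. With concordant Hgb, the Week 4 miscount therefore occurs exactly when the rise exceeds 2.0.

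**Hypothetical subjects run through Table 5 (HemoCue and central Hgb equal):**

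| Hgb by visit | Dose, mg | SAP count | Count strictly before |
|---|---|---|---|
| 9.3, 10.3 | 4, 4 | 0 | 0 |
| 9.5, 10.8 | 4, 4 | 0 | 0 |
| 8.2, 10.4 | 4, 2 | 1 | 0 |
| 9.8, 12.1 | 4, 2 | 1 | 0 |
| 9.5, 13.2 | 4, 0 | 1 | 0 |
| 9.0, 9.2, 10.1 | 4, 6, 6 | 1 | 1 |
| 8.0, 8.3, 10.6 | 4, 6, 4 | 2 | 1 |

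A subject who first reaches target at Week 24 is unaffected, because the illustration shows no dose and no flag for that visit.

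**Size at Week 4.** Inputs are the mean change of 0.5 g/dL (Protocol 4.5), SD 1.0 or 1.5 (Protocol Table 9), 20 subjects at Week 4 (Protocol Table 1) and entry Hgb of 8.0 to below 10.0 (Protocol 5.1). Normality and the baseline shape are my assumptions.

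- P(rise > 2.0) = 1 − Φ((2.0 − 0.5)/SD). For SD 1.0 this is 1 − Φ(1.5) = 6.7%. For SD 1.5 it is 1 − Φ(1.0) = 15.9%.
- From a baseline of at least 8.0, a rise above 2.0 always takes Hgb past 10.0, so these are also the probabilities of reaching target and being miscounted. Of 20 subjects: 20 × 0.067 = 1.3, and 20 × 0.159 = 3.2.
- P(reach 10.0 at Week 4) is the average over baseline b of 1 − Φ((10.0 − b − 0.5)/SD).

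| Assumed baseline | SD | P(reach) | P(miscounted) | Share of Week 4 responders |
|---|---|---|---|---|
| Uniform 8.0–10.0 | 1.0 | 0.334 | 0.067 | 20% |
| Uniform 8.0–10.0 | 1.5 | 0.378 | 0.159 | 42% |
| Uniform 9.0–10.0 | 1.0 | 0.500 | 0.067 | 13% |
| Uniform 9.0–10.0 | 1.5 | 0.500 | 0.159 | 32% |

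The complement, 58% to 87% of Week 4 responders, is correctly counted as zero.

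**The case against.** **Most responders are counted correctly.** A reader might infer that everyone who succeeds on the starting dose is reported as having needed an adjustment. Table 5 does not support that: an ordinary responder keeps the dose and scores zero. This stands and limits the point.

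**The word record may mean something else.** The SAP also uses it for a dosing interval; the Week 4 compliance formula in 10.6.2 uses the start and stop dates of the Day 1 record. If the record that achieved the target is the interval in force when it was reached, a Week 4 responder's record is Day 1 and the count is right. But the visit that opens that interval already lies before the target date, so the added clause would do nothing. The more natural reading is the visit row, and the sentence needs changing under either.

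**Disagreement between Hgb sources.** A reader might add cases where HemoCue is still below 10.0 with a rise below 0.5, so the dose goes up, while the central value is already 10.0 or more. The documents do not settle whether this can arise. SAP 10.6.3 defaults to central laboratory Hgb for reporting. SAP Table 4 note [5] and the dose-adjustment text in 8.1.2 use HemoCue. The 8.1.2 paragraph on this summary says only that on-therapy Hgb is used. If HemoCue sets the date, this route closes. The documents also give no figure for device disagreement, so I put no number on it.

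**The magnitude may be lower.** Protocol 4.5 chose 4 mg expecting no rapid rise above 2 g/dL in 4 weeks. If that held for every subject, the Week 4 miscount with concordant Hgb would be nil. The figures above follow from Table 9's SDs under normality.

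**Little depends on it.** SAP Appendix 16 shows that the summary was added in V1.2 to ease review. It is not a protocol endpoint and has no titled table in 10.14.4. Over-responders are visible in the primary endpoint's category above 2 g/dL, and dose changes are also shown by visit. This stands and sets the severity.

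**Conclusion.** The rule is wrong as written: it counts a dose decision made after the target was met. The error is upward only, at most one per subject, and confined to subjects whose dose is changed at the reaching visit. At Week 4 it would affect about 1 to 3 of 20 subjects, given a mean change of 0.5, SD 1.0 or 1.5, normality and concordant Hgb. The corresponding share of Week 4 responders, 13% to 42%, also depends on the assumed baseline distribution. Later responders who overshoot would add to this and are not in these figures.

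The stronger readings, that starting-dose successes in general are misreported or that source disagreement certainly enlarges the error, are not supported. No test, confidence interval or decision uses this count, so the severity is minor.

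**What to change.** In SAP 10.6.3, replace the rule with: count adjustment flags equal to Y only at visits strictly before the visit at which Hgb first reaches 10.0 g/dL; the flag on the reaching record is not counted. Name the Hgb source (central laboratory or HemoCue) that sets this date. While editing, settle whether unscheduled HemoCue values enter the dose-adjustment summaries, since SAP 8.1.2 and Table 4 note [5] include them and 10.6.3 excludes them.

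The cost of the counting change is one sentence and one inequality in the program. It needs no new data and does not touch patient management. With the reaching date unchanged, counts can only stay the same or fall by one.
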